## SCHEMA

## LIST OF ABBREVIATIONS AND DEFINITION OF TERMS

AE	Adverse Event
AUC	Area Under the Curve
CART	Classification And Regression Tree
CEUS	Contrast-Enhanced Ultrasound
CR	Complete Response
CRF	Case Report Form
CT	Computed Tomography
CTCAE	Common Terminology Criteria for Adverse Events
CTLA-4	Cytotoxic T-Lymphocyte-Associated Protein 4
DSMC	Data and Safety Monitoring Committee
FDA	United States Food and Drug Administration
GCP	Good Clinical Practice
ICI	Immune Checkpoint Inhibitor
IDE	Investigational Device Exemption
IRB	Institutional Review Board
Lasso	Least absolute shrinkage and selection operator
LEAD	Long Ensemble Angular-coherence Doppler
mRCC	Metastatic Renal Cell Carcinoma
OS	Overall Survival
PD	Progressive Disease
PD-1	Programmed Cell Death Protein-1
PD-L1	Programmed Death Ligand-1
PET	Positron Emission Tomography
PFS	Progression-Free Survival
PR	Partial Response
RECIST	Response Evaluation Criteria In Solid Tumors
RCC	Renal Cell Carcinoma
SAE	Serious Adverse Event
SD	Stable Disease
SOP	Standard Operating Procedure
SRC	Scientific Review Committee
TKI	Tyrosine Kinase Inhibitor
VEGFR2	Vascular Endothelial Growth Factor Receptor 2

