### 10.3.2 Analysis Plan

To address our primary objective, we will conduct a Least absolute shrinkage and selection operator (Lasso) regression as our primary analysis. Specifically, our outcome, initial objective response, will be regressed on the change in each of the LEAD ultrasound tumor perfusion parameters after 3 weeks of treatment and relevant demographic and clinical characteristics. The measurement of LEAD ultrasound tumor perfusion parameters and the definition of their change are described in more detail below. We will not use selection techniques to choose variables. Rather, we will include all factors in our model jointly. We will evaluate the predictive ability of our model using area under the curve (AUC) and calculate a 95% confidence interval for the AUC. Since our sample size is too small to allow for separate training and testing datasets, we will utilize cross-validation techniques for evaluating predictive performance.

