#### Quantification of tumor perfusion parameters:

The following parameters are computed from the LEAD ultrasound measurements for each lesion:

- overall tumor perfusion: the integrated power within the tumor
- average red cell flux: the integrated power within the tumor normalized by tumor size
- tumor-to-background perfusion ratio: the ratio of the integrated power within the tumor to the integrated power in a same sized region in nearby healthy tissue.

Changes in tumor perfusion parameters after 3 weeks of treatment:

Defined as relative change in these parameters, i.e., difference between time points divided by value at time point 1, expressed as percentage. For determining the relative change in several lesions of the same patient, the average of the relative changes in the up to 5 individual lesions is calculated.

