## **10.5 Sample Size**

Since this is an exploratory pilot study and we are not formally testing a specific research hypothesis, the sample size for each arm has been chosen based on practical considerations and estimated feasibility. However, for the primary analysis (arm 1), we consider a predictive model with a true AUC of at least 0.7 promising for predicting initial objective response. With 20 patients and assuming that 59% of patients have an objective response to treatment, a predictive model with a true AUC of at least 0.7 will have a margin of error of 0.14 so that the empirically determined AUC can range from 0.56 to 1.

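### Section 10.3.2 names a lasso as the primary analysis but says no selection technique will be used; the fitted model will rarely contain every factor and may contain no LEAD parameter

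*Protocol*

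**What the plan says.** Section 1.1 asks whether 3-week changes in LEAD perfusion parameters predict objective response at 12 weeks in arm 1. For this, section 10.3.2 states: "we will conduct a Least absolute shrinkage and selection operator (Lasso) regression as our primary analysis". The list of abbreviations gives the same expansion of the name, "Least absolute shrinkage and selection operator". The outcome "will be regressed on the change in each of the LEAD ultrasound tumor perfusion parameters after 3 weeks of treatment and relevant demographic and clinical" covariates, which are neither listed nor counted there. The paragraph continues: "We will not use selection techniques to choose variables". The sentence after that one reads: "Rather, we will include all factors in our model jointly". Performance is then judged by a cross-validated AUC with a 95% confidence interval.

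Three LEAD parameters are defined under the quantification heading of 10.3.2: integrated power in the tumor, that power normalized by tumor size, and the ratio of tumor power to power in nearby healthy tissue. Section 10.4.2 applies the same approach to the 6-week LEAD and power Doppler models and compares their AUCs by DeLong's method. Section 10.7 lets any predictive model with an AUC of at least 0.7 lead to a follow-up study.

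**The concern.** The paragraph names a method whose defining property is selection and then denies that selection takes place. Someone who reads the result with the protocol in hand would take the AUC to come from a model holding the three LEAD changes and every covariate. The lasso does not guarantee that.

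What is at stake is the meaning of the primary result. If the penalty removes all three LEAD terms, what remains is a covariate model or an intercept. An intercept-only model carries no discrimination, but a covariate-only model could reach 0.7, meet the criterion in section 10.7 and be reported as support for ultrasound. The modality comparison in 10.4.2 is exposed in the same way: if the LEAD and power Doppler models both shrink to the same covariates, their AUCs coincide and the comparison says nothing about modality.

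**Working it through.** **The plan's own figure.** The protocol gives no figure for how many factors the model will contain. Its only design figure, the AUC margin of 0.14 in section 10.5, concerns precision. It is a separate matter and is not used here.

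**Why the two statements conflict.** The logistic lasso minimises

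−(1/n)·log-likelihood(β) + λ·Σ|βⱼ|.

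At the solution, βⱼ = 0 whenever |xⱼᵀ(y − p̂)|/n falls short of λ. At λ = maxⱼ|xⱼᵀ(y − ȳ)|/n, every coefficient is zero. The protocol fixes no penalty small enough to keep all coefficients non-zero.

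**Inputs from the protocol.**
- n = 20 with 59% responders (section 10.5): 0.59 × 20 = 11.8, taken as 12 responders and 8 non-responders.
- 3 LEAD parameters (10.3.2).
- True AUC 0.7 (10.5).

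**Inputs assumed, because the protocol does not give them.**
- Pairwise correlation 0.6 among the LEAD changes.
- Signal shared equally by the three.
- 0, 2, 5 or 8 covariates without effect.
- λ chosen at the minimum 5-fold cross-validated deviance.

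**Simulation 1: lasso fitted to all 20 patients.**

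| Candidates | True AUC | Replicates | Mean number kept | All kept | None kept |
|---|---|---|---|---|---|
| 3 (LEAD only) | 0.7 | 100 | 0.94 | 8% | 46% |
| 3 (LEAD only) | 0.8 | 100 | 1.51 | 13% | 18% |
| 5 | 0.7 | 100 | 1.19 | 1% | 44% |
| 8 | 0.7 | 40 | 1.95 | 0% | 32.5% |
| 11 | 0.7 | 40 | 2.35 | 0% | 40% |

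In the rows with 3 candidates, none kept is the same as all LEAD parameters dropped. In the other rows it is a lower bound for that event, since a fit may also keep covariates alone.

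Monte Carlo error: for 46% of 100 the standard error is √(0.46 × 0.54/100) = 0.05; for 32.5% of 40 it is √(0.325 × 0.675/40) = 0.07. Zero in 40 is compatible with a true rate of up to about 3/40 = 7.5%.

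**Simulation 2: inside cross-validation.** Same 12/8 split, 4 covariates without effect, 5 outer and 4 inner folds (so each outer fit uses 20 × 4/5 = 16 patients), 60 replicates per setting.

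| LEAD signal | Correlation | Folds with all LEAD dropped | AUC, lasso minus ridge |
|---|---|---|---|
| Shared by all three | 0.6 or 0.9 | about 50% | about −0.07 to −0.08 (SE 0.02) |
| In one parameter | 0.3 | 45% | −0.02 (SE 0.024) |
| In one parameter, stronger | 0.3 | 24% | +0.03 (SE 0.021) |

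**How related the LEAD parameters are.** All three share one numerator. For a single lesion, the follow-up-to-baseline ratio of flux equals the power ratio divided by the size ratio, and that of tumor-to-background equals the power ratio divided by the background ratio. Section 2.4 says definitive diameter change takes about 12 weeks, so a size ratio near 1 at week 3 is plausible and the changes in overall perfusion and flux could be close. The protocol reports no correlations, and averaging over up to 5 lesions further separates the patient-level values from this identity.

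**The case against.** The best defence is that the sentences mean something narrower. The second begins with a contrast, which can be read as setting joint entry against stepwise or univariate screening: all candidates go into one lasso and nothing is filtered beforehand. That is a sensible plan and may well be what was intended. The method is also named plainly and more than once, so an analyst would run a lasso. Both points stand. They show that the method is not in doubt. They do not make the no-selection statement true of the fitted model, and no section confines it to pre-screening.

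A reader might infer that the plan promises a non-zero coefficient for every factor. It does not: it says factors are included, not that they are retained. A reader might also infer that strong collinearity is established; it is plausible from the definitions but not documented. Last, a reader might infer that ridge should replace the lasso because it predicts better. Simulation 2 shows an advantage when the signal is shared and no clear difference when one parameter carries it, so this is not general.

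It is also fair that a lasso which drops every LEAD term is itself informative about the primary objective, that this is a pilot without formal hypothesis testing, and that section 10.7 requires validation in an independent cohort. These limit the consequence. The first holds only if the dropping is reported, which the present wording would lead no one to expect.

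**Conclusion.** The point holds as a misstatement in the definition of the primary analysis. That a lasso selects needs no assumption. How often it does so here rests on the assumed correlation, signal, covariate number and tuning rule. Across the settings tried, every factor survived in 0% to 13% of fits in simulation 1, and all three LEAD parameters were lost in 18% to about 50% of fits or folds where that was measured directly.

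The documents do not support going further. They do not show that the lasso is the wrong method, that the analyst cannot tell which model to fit, or that ridge is what the text intends. The defect is that an AUC from a model without ultrasound terms could be presented, on the protocol's own wording, as evidence about LEAD.

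**What to change.** Replace the two sentences in section 10.3.2 with wording such as:

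> All prespecified candidates enter the lasso together without prior stepwise or univariate screening; the lasso may set some coefficients to zero, and penalty tuning and selection are repeated within each cross-validation fold.

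Add that the report will state how often each LEAD parameter is retained across folds, and that the AUC will not be attributed to LEAD when none is retained. The models in section 10.4.2 that reuse this approach, and the 0.7 criterion in 10.7, should be read under the same rule.

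If the sponsor does mean every factor to stay in the model, it should name a method that does not select, such as ridge-penalised logistic regression, and say so before the analysis. Ridge would give no short list of variables.

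The cost is an edit to one paragraph and a little more reporting, with the same data. The conclusion about LEAD may turn out less favourable.

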#### Selection of lesions for LEAD ultrasound exams:

Before the first ultrasound exam, the treating medical oncologist, a Protocol Director, or a designated radiologist selects up to 5 lesions per patient (target lesions per RECIST v1.1). At the treatment 'baseline' LEAD ultrasound exam (up to 28 days prior to start of treatment), perfusion of these 5 lesions is measured. Additional lesions may be assessed at the discretion of the investigators, so that in the end up to 5 lesions are selected for repeat ultrasound exams that in the opinion of the investigators lend themselves to reproducible tumor perfusion measurements. LEAD ultrasound tumor perfusion measurements of the up to 5 lesions that were selected for ultrasound studies at the treatment 'baseline' exam are performed again 3 weeks (+/- 8 days) after start of treatment.

#### Quantification of tumor perfusion parameters:

The following parameters are computed from the LEAD ultrasound measurements for each lesion:

- overall tumor perfusion: the integrated power within the tumor
- average red cell flux: the integrated power within the tumor normalized by tumor size
- tumor-to-background perfusion ratio: the ratio of the integrated power within the tumor to the integrated power in a same sized region in nearby healthy tissue.

Changes in tumor perfusion parameters after 3 weeks of treatment:

Defined as relative change in these parameters, i.e., difference between time points divided by value at time point 1, expressed as percentage. For determining the relative change in several lesions of the same patient, the average of the relative changes in the up to 5 individual lesions is calculated.

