### 9.1.1 Measurement Methods

Tumor diameter measurements: Where possible, the same lesions that were selected for repeat LEAD ultrasound exams are used as target lesions for response evaluation per RECIST. Different lesions may be selected at the discretion of the radiologist designated to review response evaluation.

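### Overall tumor perfusion equals red cell flux times tumor size, so the joint primary model can carry early shrinkage, and without a size-only benchmark an AUC of 0.7 cannot be attributed to perfusion

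*Protocol*

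**What the plan says.** Three LEAD parameters are computed for each lesion (Protocol 10.3.2, quantification of tumor perfusion parameters):

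- "overall tumor perfusion: the integrated power within the tumor"
- "average red cell flux: the integrated power within the tumor normalized by tumor size"
- a tumor-to-background measure, defined as "the ratio of the integrated power within the tumor to the integrated power in a same sized region in nearby healthy tissue"

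The change in each is relative: "difference between time points divided by value at time point 1, expressed as percentage". With several lesions, "the average of the relative changes in the up to 5 individual lesions is calculated". The primary lasso regresses response on all three changes together with demographic and clinical characteristics: "Rather, we will include all factors in our model jointly". Performance is a cross-validated AUC.

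The outcome is CR or PR per RECIST v1.1 at 8-16 weeks (section 9.1). On lesions, section 9.1.1 says: "Where possible, the same lesions that were selected for repeat LEAD ultrasound exams are used as target lesions for response evaluation per RECIST". Section 10.7 makes an AUC of at least 0.7 the minimum for a follow-up study, and any predictive model from the pilot can meet it. No model based on size change alone is named as a comparator. The protocol does not say whether tumor size is a diameter, an area or a volume, or whether the outline is redrawn at each exam.

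**The concern.** The first two predictors are built from the same power reading and differ only by tumor size. A model that holds both changes can recover the size change between baseline and week 3. Response at 12 weeks is itself a size change, largely in the same lesions, so the predictor set may contain an early reading of the outcome.

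The primary objective asks whether perfusion changes predict response. If early shrinkage supplies the discrimination, the trial could call LEAD perfusion promising when a size measurement at the same exam would have done as well. No planned result would show the difference.

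The exploratory correlations in section 10.4.2 share the problem. Overall perfusion contains lesion size and is correlated with change in that lesion's diameter and in tumor burden.

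**Working it through.** **Plan's own figure.** The only related figure is the 0.14 margin of error in section 10.5. The Hanley-McNeil standard error at AUC 0.7 with 12 responders and 8 non-responders (59% of 20) is 0.118, so the 95% half-width is 1.96 × 0.118 = 0.23. The 0.14 is not reproduced. That is a separate matter and this point does not depend on it, but the standard error matters for the fix.

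**Algebra from the definitions.** Let P be overall perfusion, F flux, S tumor size, and d a relative change from baseline to week 3.

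- F = P / S, so P = F × S.
- Per lesion: (1 + dP) = (1 + dF) × (1 + dS).
- Hence (1 + dP) / (1 + dF) = 1 + dS exactly, and dP − dF = (1 + dF) × dS.
- The third parameter uses a background region of equal size, so size cancels.

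Example, taking size as an area and perfusion density as unchanged: a 10% fall in diameter gives dS = 0.9² − 1 = −19%, so dP = −19% and dF = 0.

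Averaging over lesions does not remove this. In simulation with 3 or 5 lesions per patient, the ratio of averaged changes correlated above 0.999 with mean size change, and the linear contrast dP − dF correlated 0.88-0.89.

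**If the outline is fixed at baseline.** S is then constant and dP = dF for every lesion. No size signal enters, but two of the three predictors are the same variable.

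**How far shrinkage alone can take the AUC.** Perfusion density was simulated as pure noise, unrelated to response. Inputs from the protocol are N = 20 and 59% responders. Assumptions not in the protocol:

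- SD of log-diameter change 0.25 at week 12 and 0.08 at week 3
- SD of log perfusion density 0.3
- no size measurement error
- power scaling with the chosen size measure (diameter, area or volume)
- week-3 to week-12 size correlation varied from 0 to 0.85

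The true AUC comes from 300,000 simulated patients. The N = 20 columns come from 300 trials per setting; the lasso used nested 5-fold cross-validation, and size change alone was used directly as a score.

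| Assumed size correlation | True AUC, three LEAD changes | True AUC, flux and ratio only | N = 20: lasso reaches 0.7 | N = 20: size change alone reaches 0.7 |
|---|---|---|---|---|
| 0 | 0.50 | 0.50 | about 3% | 4-6% |
| 0.3 | 0.63 | 0.50 | not run | not run |
| 0.45 | 0.70 | 0.50 | not run | not run |
| 0.5 | 0.72-0.73 | 0.50 | 8-12% | 62% |
| 0.7 | 0.82-0.83 | 0.50 | 24-37% | 88-91% |
| 0.85 | not run | not run | 55-66% | 98% |

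Without overall perfusion, the lasso on flux and ratio reached 0.7 in 3-5% of trials. With an almost unpenalized fit of all three changes, the shares at correlations 0, 0.5, 0.7 and 0.85 were 6-7%, 23-25%, 52-55% and 80-81%, so the penalty matters. Doubling the density SD to 0.6, in a population run with 41% responders, lowered the true AUC by at most 0.012.

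**What correlation is plausible.** The protocol gives none. As a reference only, independent equal weekly increments would give √(3/12) = 0.5 at week 3 and √(6/12) = 0.71 at week 6. On that basis the 6-week models in section 10.4.2 are more exposed than the primary one.

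**The case against.** Four points on the other side carry weight.

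1. **The early size signal may be weak.** Section 2.4 says definitive diameter changes on CT take about 12 weeks. Size measurement error would weaken the signal further. Small changes can still rank patients, but this argues against assuming a high correlation.
2. **The lasso resists the size contrast.** P and F must enter with opposite signs, which the penalty discourages at N = 20. The table shows this: at correlation 0.5, 8-12% of trials pass against 62% for size alone.
3. **The leak needs re-outlining at week 3.** That is the natural reading of power within the tumor, but it is an inference. Outlining rules and sensitivity models could sit in an analysis plan or imaging manual not shown. However, the protocol itself fixes the predictors, their joint entry and the 0.7 criterion.
4. **The stakes are limited.** This is a pilot with no formal hypothesis test. Passing leads to an independent validation cohort, and a size benchmark could be added to the same data later.

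A reader might infer that the primary model will probably pass on shrinkage alone. Pass rates of 67% and 93% can be obtained if week-3 shrinkage is a fixed 25% or 40% of the week-12 change (SD 25 points) plus 5 points of error, with a light fixed penalty of 0.02. Those settings imply correlations of 6.25/√(6.25² + 5²) = 0.78 and 10/√(10² + 5²) = 0.89. The protocol supports neither the correlations nor the penalty.

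A reader might also infer that overall perfusion must leave the main model, or that LEAD must beat size before any claim. Neither follows. Total perfusion can legitimately reflect vascular volume, and with an AUC standard error of about 0.12 a superiority requirement is unworkable at N = 20.

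**Conclusion.** The structural point holds. If the tumor is re-outlined, the joint model carries week-3 shrinkage, the outcome is shrinkage of largely the same lesions, and no planned result separates the two. Under the plan as written, an AUC of 0.7 or more could not be attributed to perfusion. If the outline is fixed, one predictor is redundant instead. Either way the definition needs attention.

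The practical size is conditional. The true AUC reaches the threshold without perfusion information at a size correlation of about 0.45, but the chance that the planned week-3 lasso does so in 20 patients runs from about 3% to 55-66% over correlations of 0 to 0.85. The protocol does not place the trial within that range, and section 2.4 leans toward its lower part. Should-fix.

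**What to change.** In sections 10.3.2 and 10.7:

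- State how tumor size is measured and that the outline is redrawn at each exam. Flux is free of size only if size is measured in the same dimensions over which power is integrated. If the outline is instead kept fixed, say so and keep only one of the two identical changes.
- Report the AUC of week-3 size change alone, under the same cross-validation, beside the LEAD model.
- Report a companion model with only the size-normalized parameters (flux and tumor-to-background ratio).
- Attribute an AUC of at least 0.7 to perfusion only in light of these results. Show the difference from size alone with its interval, descriptively and not as a formal superiority test.

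In section 10.4.2, do the same for the 6-week models, and note that correlations of overall perfusion with diameter change include a built-in size component.

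The cost is a little more analysis and a possibly less favourable conclusion. No new patients or exams are needed, because size is already required to compute flux.

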## 10.4 Secondary Analysis

### 10.4.1 Analysis Population

All patients who have completed at least one LEAD and Doppler ultrasound exam at any time point. For correlation analyses, patients are included for each analysis based on availability of data points for specific analyses. If fewer than 20 patients in arm 1 and 10 patients in arm 2 fulfill these criteria for any secondary analysis, additional patient may be enrolled at the discretion of the Protocol Directors to have a complete dataset from 20 and 10 patients for this analysis, respectively.

### 10.4.2 Analysis Plan

To address our secondary objective, i.e., evaluating if there is an optimal ultrasound modality to predict initial objective response in arm 1, we will utilize the same analysis approach as outlined above for the primary analysis. Here, we will use change in tumor perfusion parameters at **6 weeks** as our independent variables and conduct two regression analyses: (1) using power Doppler measurements and (2) using LEAD ultrasound measurements. AUCs between the two models will be compared using the nonparametric approach of DeLong for correlated AUC curves. In addition, we will compare AUCs between these models to the predictive model for the primary analysis.

To assess if there is an optimal time point for predicting initial objective response in arm 1, we will conduct Lasso regression models using tumor perfusion parameters for each time point (treatment 'baseline', 3 weeks, 6 weeks) separately for each imaging modality using a similar approach as outlined above. Given the exploratory nature of these analyses, we will not adjust for multiple testing.

For each arm, we will conduct correlation analysis for change in perfusion parameters at 3 and 6 weeks and initial relative change in tumor burden (overall and per-lesion), initial overall response, best overall response, and PFS until 12 months after initiating treatment by calculating either the Pearson r or Spearman rank correlation, as appropriate. PFS is estimated using the Kaplan-Meier method and the Kaplan-Meier curves will be presented.

Selection of lesions for ultrasound exams:

The up to 5 lesions that were selected for ultrasound studies for the primary analysis are re-assessed 6 weeks (+/- 15 days) after start of treatment and each lesion is assessed with both LEAD and power Doppler ultrasound at all 3 time points (treatment 'baseline', 3 weeks, and 6 weeks after initiating treatment).

Quantification and change of tumor perfusion parameters: defined in the same way as for the primary analysis for both power Doppler and LEAD ultrasound.

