### 1.2 Secondary Objectives

Our secondary objectives are to evaluate in arm 1, if there is an optimal ultrasound imaging modality (power Doppler or LEAD ultrasound), or optimal time point to predict initial objective response. We will assess how well 1) changes in tumor perfusion parameters 6 weeks after start of treatment by imaging modality or 2) tumor perfusion parameters at a single time point (treatment 'baseline', 3 weeks, or 6 weeks after start of treatment), predict initial objective response (at 12 weeks) per RECIST v1.1.

Additional exploratory objectives in both arms are to assess the correlation of tumor perfusion parameters with change in overall tumor burden (defined as sum of the longest diameters of all measurable lesions defined by RECIST v1.1) 12 weeks after start of treatment, with change in diameter on a per-lesion basis (correlation between perfusion parameters of a single lesion with change in diameter of that lesion), and with 12-month progression-free survival (PFS).

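### Should LEAD and power Doppler also be compared on change at 3 weeks, when the plan compares them on change only at 6 weeks?

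*Protocol*

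**What the plan says.** The primary analysis (Section 10.3.2) is a Lasso regression in which initial objective response "will be regressed on the change in each of the LEAD ultrasound tumor perfusion parameters after 3 weeks of treatment", together with demographic and clinical characteristics. Its performance is summarised by a cross-validated AUC.

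Section 1.2 asks in general terms whether one modality or one time point is best. It then names two things to assess. The first is how well "changes in tumor perfusion parameters 6 weeks after start of treatment by imaging modality" predict response. The second is how well parameters at a single time point do so.

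Section 10.4.2 follows that split:

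- For modality, it takes 6-week change "as our independent variables and conduct two regression analyses: (1) using power Doppler measurements and (2) using LEAD ultrasound measurements", and compares the two AUCs by DeLong's method. It adds: "In addition, we will compare AUCs between these models to the predictive model for the primary analysis".
- For time point, it fits Lasso models on the parameter values at baseline, 3 weeks and 6 weeks, "separately for each imaging modality using a similar approach as outlined above".
- In each arm, "we will conduct correlation analysis for change in perfusion parameters at 3 and 6 weeks", against tumour burden, response and PFS.

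The data for both modalities are scheduled throughout: "each lesion is assessed with both LEAD and power Doppler ultrasound at all 3 time points". Perfusion parameters and their change are "defined in the same way as for the primary analysis for both power Doppler and LEAD ultrasound".

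**The concern.** The primary predictor is change at 3 weeks, and the purpose of the trial is early detection of response. One would expect the two modalities to be set against each other on that same predictor at that same visit. The protocol does so on the change scale only at 6 weeks.

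The comparison of the 6-week models with the primary model seems to make this worse. For power Doppler it sets a 6-week model against a 3-week LEAD model, so modality and time differ together and a difference belongs to neither alone.

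If this were a true flaw, the trial could collect power Doppler at 3 weeks, fail to use it for its own modality question, and carry a LEAD model forward under Section 10.7 without knowing whether the commercially available mode does as well at the same visit.

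**Working it through.** **1. Count the planned Lasso models (Sections 10.3.2 and 10.4.2).**

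| Predictor | LEAD | Power Doppler |
|---|---|---|
| Change at 3 weeks | yes (primary) | none named |
| Change at 6 weeks | yes | yes |
| Value at baseline | yes | yes |
| Value at 3 weeks | yes | yes |
| Value at 6 weeks | yes | yes |

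That is 1 + 2 + 6 = 9 models. Of the 2 × 2 = 4 change models, 3 are planned. The factual premise is correct.

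**2. Set objective and analysis side by side.** Section 1.2 places change by modality at 6 weeks. Section 10.4.2 fits exactly those two models and compares their AUCs. The other part of the objective, single time points, is covered by the six value models. No analysis that the objective asks for is missing, and the two sections agree.

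**3. What is done with power Doppler at 3 weeks.** Its values enter a Lasso model of their own, under an approach that ends in an AUC, beside the matching LEAD model. Its change enters the correlation analysis, which covers change at 3 and 6 weeks and is not restricted to one modality. Only the combination of power Doppler, 3 weeks, change scale and AUC is absent.

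**4. The mixed contrast.** Write P6 for the AUC of power Doppler change at 6 weeks, and L6 and L3 for LEAD change at 6 and 3 weeks. Then

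P6 − L3 = (P6 − L6) + (L6 − L3).

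The first bracket is modality at a fixed time and the second is time within a fixed modality. Both are planned. A reader can therefore see how much of the mixed difference comes from each. The split is exact when the three AUCs come from the same patients, and approximate if the patient sets differ. The protocol nowhere says that the mixed contrast will be read as an effect of modality or of time.

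**5. What the absent comparison could have shown.** The inputs from Section 10.5 are 20 patients, 59% responders (0.59 × 20 = 11.8, taken as 12, leaving 8 non-responders) and AUC 0.7. The correlation r between the two AUCs is not in the protocol and is assumed. The Hanley–McNeil variance is

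[A(1 − A) + (m − 1)(Q₁ − A²) + (n − 1)(Q₂ − A²)] / (mn),

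with Q₁ = A/(2 − A) = 0.7/1.3 = 0.5385 and Q₂ = 2A²/(1 + A) = 0.98/1.7 = 0.5765. With m = 12 and n = 8:

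[0.21 + 11 × 0.0485 + 7 × 0.0865] / 96 ≈ 0.0140, so SE = 0.1185.

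The 95% half-width of the AUC difference is 1.96 × SE × √(2(1 − r)):

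| Paired patients | SE | r = 0 | r = 0.5 | r = 0.9 |
|---|---|---|---|---|
| 20 (12/8) | 0.1185 | 0.33 | 0.23 | 0.10 |
| 14 (8/6) | 0.1430 | 0.40 | 0.28 | 0.13 |

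The row for 14 is an assumed case of incomplete pairing. The Section 6 calendar (footnote a) allows for an exam done with only one scanner, and the primary population requires only the LEAD exams. At r = 0.5 and full pairing, the half-width of 0.23 exceeds the whole distance from the promising AUC of 0.7 to chance, 0.7 − 0.5 = 0.20. The formula treats the model scores as fixed, so variability from refitting the Lasso in cross-validation comes on top.

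**The case for a change.** The best case for a finding runs as follows. The protocol does not leave this open for an analysis plan: it names 6 weeks and two regressions. Values at 3 weeks are not change at 3 weeks, and a correlation coefficient is not a cross-validated AUC, so neither stands in for the absent model. Section 10.7 carries forward the model with the best AUC, and power Doppler change at 3 weeks cannot be chosen because it is never fitted. The imprecision above applies equally to the planned 6-week comparison, so it is no reason to leave out only the 3-week one. The extra model would need no new exam and no new patient.

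Much of this stands as description. The cell is empty. The modality difference on the change scale at 3 weeks cannot be recovered from the other three cells unless one assumes that it is the same at both times. The imprecision shows how little is forgone; it does not justify the choice of 6 weeks.

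It does not follow that the plan is wrong. Section 1.2 asks the change-by-modality question at 6 weeks, and a design may limit an exploratory question in this way. Section 10.1 labels the secondary endpoints exploratory and hypothesis-generating, and Section 10.4.2 makes no multiplicity adjustment for these analyses. A tenth Lasso model in about 20 patients would add one more candidate to the AUC threshold and best-AUC choice of Section 10.7. If it were kept out of that rule to avoid this, it would inform no decision that the protocol describes. As both scanners are scheduled at every visit, the comparison can still be made later on the patients with both exams.

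**Conclusion.** The concern does not hold. The protocol names no Lasso model on 3-week power Doppler change, so 3 of 4 change models are planned. But this matches the objective in Section 1.2, contradicts nothing elsewhere, and leaves the primary analysis unaffected. Followed as written, the plan answers the modality question it sets, and the contrast that mixes modality with time can be read through two planned contrasts that do not.

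What is forgone is one exploratory comparison with a 95% half-width of about 0.23 at an assumed correlation of 0.5 with 20 paired patients. The range is 0.10 to 0.40 over assumed correlations of 0 to 0.9 and 14 to 20 paired patients. These figures rest on both AUCs being 0.7, on 59% responders, and on assumed values for the correlation and the number paired. The conclusion itself rests on the agreement of Sections 1.2 and 10.4.2 and not on these figures. No change to the protocol is needed.
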